## 7.0 RECRUITMENT PLAN

Patients will be recruited from the patients seen by the Gynecologic Medical Oncology (GMO) Service, Department of Medicine, at Memorial Sloan-Kettering Cancer Center (MSKCC). The investigator will screen patients with ovarian, primary peritoneal and fallopian tube cancer to see if they are eligible for this trial.

During the initial conversation between the investigator/research staff and the patient, the patient may be asked to provide certain health information that is necessary to the recruitment and enrollment process. The investigator/research staff may also review portions of their medical records at MSKCC in order to further assess eligibility. They will use the information provided by the patient and/or medical record to confirm that the patient is eligible and to contact the patient regarding study enrollment.

## 8.1 PRETREATMENT EVALUATION

### Screening:

- Signature of *screening informed consent*
- Tumor biopsy or paracentesis, if no archival tissue is available
- Verification of  $\geq$ 5% AR+ by IHC in tumor tissue

### To be completed within 30 days prior to start of study drug:

- Signature of *treatment informed consent* following inclusion and exclusion review and determination of patient eligibility for the study
- Physical exam and vital signs (height, weight, pulse, temperature, blood pressure)
- Karnofsky Performance Status (KPS)
- 12-lead ECG
- Baseline radiographic tumor assessment (CT or MRI of abdomen and pelvis; CT of chest) with documentation of sites of disease per RECIST (version 1.1)

To be completed within 14 days prior to start of study drug:

- Pregnancy test in women of child bearing potential
- Blood sampling for:
  - CBC with differential
  - Comprehensive Metabolic Panel (Na, K, Cl, CO2, BUN, CREAT, Ca, Glucose, Bilirubin, total protein, albumin, alkaline phosphatase, AST, ALT)

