- Women of child bearing potential must use an effective form of contraception during study and for at least 6 months after completion of study treatment
- Recovery from effects of recent surgery, radiotherapy, or chemotherapy
  - At least 4 weeks out from their last dose of radiation therapy
  - At least 4 weeks post-op from any major surgical procedure
  - At least 3 weeks out from their last dose of chemotherapy and/or biologic/targeted therapy
- No prior hormonal therapy for treatment of cancer within the past 21 days
- Absence of any psychological, familial, sociological or geographic condition that would potentially hamper compliance with the study protocol
- Prior use of or participation in a clinical trial evaluating and agent that either blocks androgen synthesis (e.g. abiraterone acetate, TAK-700, TAK-683, TAK-448) or targets the AR (e.g., bicalutamide, BMS-641988) (patients who are known to have only received placebo in these studies are eligible)
- Laboratory Test Findings performed within 14 days prior to initiation of study drug showing:
  - Bone marrow function:
    - Absolute neutrophil count (ANC)  $\geq 1,000/\text{mcL}$
    - Platelets  $\geq 100,000/\text{mcL}$
    - Hemoglobin  $\geq 8 \text{ g/dL}$
  - Renal function:
    - Creatinine  $\leq 1.5 \times \text{ULN}$
  - Hepatic function:
    - Bilirubin  $\leq 1.5 \times \text{ULN}$
    - AST and ALT  $\leq 2.5 \times \text{ULN}$
- Resolution of all acute toxic effects of prior therapy to NCI CTCAE (Version 4.0) Grade  $\leq 1$ , with the exception of unresolved Grade 2 neuropathy and Grade 2 alopecia, which are allowed
- Patients must be able to swallow tablets whole, without crushing

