### 12.3 Methods for Evaluation of Measurable Disease

All measurements should be taken and recorded in metric notation using a ruler or calipers. All baseline evaluations should be performed as closely as possible to the beginning of treatment and never more than 4 weeks before the beginning of the treatment.

The same method of assessment and the same technique should be used to characterize each identified and reported lesion at baseline and during follow-up. Imaging-based evaluation is preferred to evaluation by clinical examination unless the lesion(s) being followed cannot be imaged but are assessable by clinical exam.

Clinical lesions: Clinical lesions will only be considered measurable when they are superficial (e.g., skin nodules and palpable lymph nodes) and  $\geq 10$  mm diameter as assessed using calipers (e.g., skin nodules). In the case of skin lesions, documentation by color photography, including a ruler to estimate the size of the lesion, is recommended.

Chest x-ray: Lesions on chest x-ray are acceptable as measurable lesions when they are clearly defined and surrounded by aerated lung. However, CT is preferable.

Conventional CT and MRI: This guideline has defined measurability of lesions on CT scan based on the assumption that CT slice thickness is 5 mm or less. If CT scans have slice thickness greater than 5 mm, the minimum size for a measurable lesion should be twice the slice thickness. MRI is also acceptable in certain situations (e.g. for body scans), but NOT lung.

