## **12.4 Response Criteria**

### **12.41 Evaluation of Target Lesions**

Complete Response (CR): Disappearance of all target lesions. Any pathological lymph nodes (whether target or non-target) must have reduction in short axis to <10 mm.

Partial Response (PR): At least a 30% decrease in the sum of the diameters of target lesions, taking as reference the baseline sum diameters.

Progressive Disease (PD): At least a 20% increase in the sum of the diameters of target lesions, taking as reference the smallest sum on study (this includes the baseline sum if that is the smallest on study). In addition to the relative increase of 20%, the sum must also demonstrate an absolute increase of at least 5 mm. (Note: the appearance of one or more new lesions is also considered progressions).

Stable Disease (SD): Neither sufficient shrinkage to qualify for PR nor sufficient increase to qualify for PD, taking as reference the smallest sum diameters while on study.

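### Sections 8.1 and 12.3 give different baseline imaging windows, and under either one the scan may precede the last dose of prior systemic therapy by 7 to 9 days

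*Combined protocol and SAP*

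**What the plan says.** Two sections set the timing of the baseline scan.

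- Section 8.1 (Pretreatment Evaluation) places the baseline tumor imaging under the heading "To be completed within 30 days prior to start of study drug".
- Section 12.3 wants baseline assessments done as near to first dose as can be managed, and sets the outer limit in these words: "never more than 4 weeks before the beginning of the treatment".

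Section 6.2 sets the minimum interval since earlier systemic treatment separately: "At least 3 weeks out from their last dose of chemotherapy and/or biologic/targeted therapy" and "No prior hormonal therapy for treatment of cancer within the past 21 days". Neither criterion mentions the scan.

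Under Section 12.41 a partial response is a fall of at least 30% in the sum of target-lesion diameters, "taking as reference the baseline sum diameters". Section 9.1 asks for best response to be confirmed by repeat imaging at least 4 weeks later. Section 14.1 treats success on either response or 6-month PFS as enough. Under Section 14.2, 3 responses among 28 patients open stage II, and 7 at the end make the trial positive.

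**The concern.** The two imaging windows cannot both govern: a scan on day −29 or −30 meets Section 8.1 and breaches Section 12.3.

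The scan window is also longer than the interval required since systemic therapy. A patient could be scanned, receive a last dose of the previous regimen and then start enzalutamide, without breaking a stated interval. Any shrinkage from that last dose would then be measured from a baseline that predates it.

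Eligibility does not clearly screen such patients out. Section 6.2 admits a patient with one prior regimen who has persistent disease, and states no requirement of progression after two or three regimens.

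The trial has no control arm in which the same carry-over would appear, and the response cut-off is low, so a few misattributed responses could affect the conclusion.

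**Working it through.** **1. Timing.** Permitted gap = (earliest allowed scan, in days before first dose) − (minimum days since prior treatment).

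| Prior treatment | Minimum interval (6.2) | Gap, 30-day window (8.1) | Gap, 4-week limit (12.3) |
|---|---|---|---|
| Chemotherapy, biologic/targeted | 21 days | 30 − 21 = 9 | 28 − 21 = 7 |
| Hormonal | 21 days | 30 − 21 = 9 | 28 − 21 = 7 |
| Radiation, major surgery | 28 days | 30 − 28 = 2 | 28 − 28 = 0 |

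For systemic therapy the gap exists whichever window governs.

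**2. Reproducing the plan's operating characteristics.** Inputs from Section 14.2: null rates 5% (response) and 15% (6-month PFS); 28 patients in stage I; continue if there are at least 3 responses or at least 5 progression-free; positive if there are at least 7 responses or at least 13 progression-free. The sample-size text gives 31 stage II patients (total 59), but Section 4.3 and the accrual paragraph of Section 14.2 give 30 (total 58).

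Let R and P be the counts of responders and of progression-free patients, with subscripts for stage. Then

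P(positive) = Σ P(R₁, P₁) × [1 − P(R₂ ≤ 6 − R₁ and P₂ ≤ 12 − P₁)],

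summed over R₁ ≥ 3 or P₁ ≥ 5. The joint probability of both outcomes in one patient is the product of the two rates (independence) or 0.90 × the smaller rate (the plan's dependence model).

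| | Plan | 28 + 30 | 28 + 31 |
|---|---|---|---|
| Type I error, independent / dependent | 0.10 / 0.09 | 0.099 / 0.090 | 0.109 / 0.099 |
| Early stopping under the null | 49% / 55% | 49% / 55% | 49% / 55% |

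The stated type I errors match 58 patients, so 58 is used below.

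**3. Sensitivity to carry-over.** The documents do not say how many patients would be scanned before a last prior dose, so k, the expected number of spurious confirmed responders per 58, is an assumption. The drug is taken as inactive and 6-month PFS stays at 15%. Apparent response rate = 0.05 + k/58.

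| k (assumed) | Apparent response rate | P(positive), independent | P(positive), dependent |
|---|---|---|---|
| 0 | 5.0% | 0.099 | 0.090 |
| 0.25 | 5.4% | 0.109 | 0.097 |
| 0.5 | 5.9% | 0.121 | 0.105 |
| 1 | 6.7% | 0.155 | 0.130 |
| 2 | 8.4% | 0.257 | 0.214 |
| 3 | 10.2% | 0.393 | 0.337 |

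For scale, the null itself implies 0.05 × 58 = 2.9 responders, so k = 3 slightly more than doubles the response count. With 59 patients and independence, k = 0 gives 0.109 and k = 3 gives 0.403; the choice of 58 or 59 does not change the picture.

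**4. How long the shrinkage must last.** With a last prior dose on day −21 and the first response scan at 8 weeks, that scan falls about 3 + 8 = 11 weeks after the dose. Confirmation at least 4 weeks later falls about 15 weeks after it.

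**The case against.** Four points can fairly be made on the other side.

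- **Other text may already forbid the sequence.** Section 6.3 excludes patients with other cancer treatment under way or expected, and Section 12.3 asks for scans close to the start of treatment. These weaken any claim that an early scan followed by chemotherapy is plainly compliant. But the exclusion can be read as applying only from enrollment, and the Section 12.3 instruction is not tied to the end of prior therapy. Neither clearly closes the gap.
- **Confirmation narrows the route.** A spurious partial response must still be present about 15 weeks after the last prior dose, and regrowth by then would defeat it. This stands: confirmation uses the same baseline, so it does not correct the carry-over, but it does filter it.
- **The bias can run the other way.** If disease grows between an early scan and first dose, the baseline sum is too small and a response is harder to reach. This also stands; the net direction is not shown by the documents.
- **The size is assumed.** This is right. At k = 0.25 or 0.5 the error stays near the design level.

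A reader might also infer that the scan could precede surgery or radiation, so that their effects would count as response. The documents do not support making that part of the point. The gap is at most 2 days, exists only under the 30-day wording and is zero under Section 12.3. The disease-parameters part of Section 12.2 also largely keeps irradiated lesions out of the measurable set, unless progression is documented or a biopsy confirms persistence.

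**Conclusion.** The point holds for prior systemic therapy only. The 30-day and 4-week windows contradict each other. Under either, the reference scan may precede the last prior chemotherapy, biologic/targeted or hormonal dose, by up to 9 or 7 days.

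The effect on the trial's conclusion cannot be estimated from the documents. The number of patients affected is unknown and probably small. The range in the working shows how sensitive a cut-off of 7 responses is to a few misattributed ones. It does not predict the trial's error rate, and its upper end should not be read as the actual type I error. It assumes an inactive drug, an unchanged PFS rate and spurious responses that survive confirmation.

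The correction is worth making because it is specific and cheap, not because a large bias has been shown.

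**What to change.** Reconcile Sections 8.1 and 12.3 to a single imaging window, and state the order of events. Suggested wording: *The baseline tumor assessment must be obtained no more than 28 days before first dose, after the last dose of any prior systemic anticancer therapy, and as close to first dose as feasible.* Cross-refer to it from Section 6.2.

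This brings the permitted gap for systemic therapy to zero. It reduces carry-over without eliminating it: a scan the day after the last prior dose would still qualify, and shrinkage after that scan would still count. The request to scan close to first dose limits this.

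The cost is a short amendment, plus retiming or repeating a few early scans. The scan fits inside the interval already required before enzalutamide starts. Sample size, cut-offs and planned power do not change.

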## 9.1 TREATMENT/INTERVENTION PLAN

Enrolled patients will initiate treatment with enzalutamide 160mg by mouth daily beginning Day 1 of Cycle 1. A Cycle is 28 days. Four 40 mg enzalutamide capsules should be swallowed whole with a glass of water. Enzalutamide should be taken at the same time each day. Missed doses will not be made-up. All doses, and missed doses will be recorded in the patient's pill diary. Patients will remain on treatment with enzalutamide 160mg PO QD (with dosage adjustments as described below) until POD, unacceptable toxicity or withdrawal of consent.

While on study, patients will return for assessments with a treating physician every 2 weeks during the first cycle, and then every 4 weeks. Vital signs, toxicity assessment and blood work will be performed at each start of cycle visit. The pill diary will be collected and a new drug supply and pill diary will be provided. A +/- 4 day window is allowed for each start of cycle assessment.

During screening, every 2 cycles (8 weeks) while on treatment, and at end of study, patients will have a CT or MRI of abdomen and pelvis performed. Best overall response should be confirmed with repeat imaging performed at  $\geq 4$  weeks. Chest imaging with CT should be performed at baseline. If initial chest imaging is abnormal or continued chest imaging is required to monitor tumor response, then it should be repeated every 2 cycles (8 weeks) while on treatment and at end of study. There is a +/- 7 day window for completion of interval tumor assessments by imaging.

Blood work will be drawn to measure levels of estradiol and testosterone on Day 1 of Cycle 1, Day 1 of Cycle 2, and at end of treatment.

An optional research non-billable tumor biopsy will be performed at end of treatment in consenting patients with accessible disease. A tube of whole blood will be drawn on Day 1 of Cycle 1 and on Day 1 of Cycle 2 for gene expression studies and cell free DNA analysis.

## 9.2 Overview of Dose Adjustments of Enzalutamide for Toxicity

Report of seizure will result in immediate cessation of enzalutamide. A patient who experiences a DLT (other than seizure) during the safety lead-in phase may be allowed to continue study treatment following adequate recovery and appropriate dose modification. Any dose modification of enzalutamide requires consultation with the study sponsor.

- If Grade 1 or 2 toxicities occur, give supportive care per institutional guidelines. No enzalutamide dose reduction should occur.
- If  $\geq$  Grade 3 toxicities occur that are considered potentially related to enzalutamide, including headache, nausea, vomiting or diarrhea, hold enzalutamide until the toxicity resolves to  $\leq$  Grade 1, unless baseline is grade 2, then until returns to baseline.
- If enzalutamide is held for  $\leq$ 28 days it may be restarted at the same or a reduced dose at the discretion of the study sponsor (or designee).
- If enzalutamide is held for  $>$ 28 days the patient should be removed from study treatment

### 9.3 Drug Interactions

Any medication (see **Appendix B** for representative medications) that may predispose the patient to seizure disorder should be stopped at least 4 weeks prior to starting treatment with enzalutamide.

The following medications or therapies are prohibited during the receipt of study drug:

- Medications, including herbal therapies, with an antitumor effect
- Any investigational agent
- AR antagonists
- 5- $\alpha$  reductase inhibitors
- Androgens
- And medication (see Appendix B for representative medications) that may predispose the patient to seizure

### 9.4 Precautions Regarding Concomitant Medications

Please refer to the following link for an up to date list of CYP and P-glycoprotein inhibitors, inducers, and substrates.

<http://www.fda.gov/Drugs/DevelopmentApprovalProcess/DevelopmentResources/DrugInteractionsLabeling/ucm093664.htm#potency>

### 9.5 Effects of Enzalutamide on Cytochrome P450 Enzymes and P-Glycoprotein

In vitro studies showed that enzalutamide is an inhibitor of CYP2C8 and CYP2C19 with lesser inhibitory effects on CYP2B6 and CYP2C9. Substrates of CYP2B6, CYP2C8, CYP2C9, and CYP2C19 that have a narrow therapeutic index (e.g., paclitaxel, phenytoin, warfarin) should be used with caution.

In vitro studies showed that enzalutamide may be an inducer of CYP3A4. Co-administration of enzalutamide with CYP3A4/5 substrates may reduce oral bioavailability and/or accelerate elimination of the CYP3A4/5 substrate.

In vitro studies showed that enzalutamide is an inhibitor of the efflux transporter P-glycoprotein (P-gp). Co-administration of enzalutamide with P-gp substrates may increase the plasma concentrations of the P-gp substrate. Use caution when co-administering P-gp substrates (e.g., digoxin, fexofenadine, paclitaxel) during enzalutamide treatment.

### 9.6 Drugs That May Increase Enzalutamide Plasma Concentrations

In vitro studies showed that enzalutamide is metabolized by CYP2C8 and CYP3A4/5. Use caution when co-administering a strong CYP2C8 inhibitor (e.g., gemfibrozil) or strong CYP3A4/5 inhibitors (e.g., clarithromycin, itraconazole, ketoconazole, grapefruit juice) during enzalutamide treatment.

### 9.7 Drugs That May Decrease Enzalutamide Plasma Concentrations

Use caution when co-administering a CYP2C8 inducer (e.g., rifampin) or strong CYP3A4/5 inducers (e.g., carbamazepine, phenytoin, rifampin, St. John's wort) during enzalutamide treatment.

### 10.0 EVALUATION DURING TREATMENT/INTERVENTION

		Screening				
		Day 1; Cycle 1	Day 15; Cycle 1	Day 1; Cycle 3, 5, 7... (odd cycles) 	Day 1; Cycle 2,4,8...(even cycles) 	End of Study Treatment
Informed Consent	X					
History & Physical Exam 	X	X	X 	X 	X 	X
Toxicity Assessment	X	X	X	X	X	X
Vital Signs	X 	X 	X 	X 	X 	X 
KPS	X	X	X	X	X	X
ECG	X 					
CT of Chest	X 			X 		X 
Radiographic Tumor Assessment of Abd/Pelvis	X 			X 		X 
CBC with Differential	X	X	X	X	X	X
Pregnancy Test (for patients of child bearing potential)	X					
Comprehensive Metabolic Panel	X	X	X	X	X	X
Liver function Tests	X	X	X	X	X	
Blood for Hormones		X			X 	X
Whole blood research test		X 			X 	
Tumor Biopsy	X 					X 
Dispense Enzalutamide		X 		X 	X 	

1: Vital signs: blood pressure, heart rate, temperature and weight. Height need only be taken on Cycle 1, Day 1.

2: Hypokalemia should be corrected prior to ECG collection

3: Chest imaging with CT should be performed at baseline. If initial chest imaging is abnormal or continued chest imaging is required to monitor tumor response, then it should be repeated every 2 cycles (8 weeks) while on treatment and at end of study. There is a +/- 7 day window for completion of interval tumor assessments by imaging.

4: Radiographic tumor assessment of abdomen and pelvis may be performed using CT or MRI. There is a +/- 7 day window for completion of interval tumor assessments by imaging.

5: Patients without adequate archival tissue available will have a biopsy performed. Patients who consent for an end of treatment biopsy will have an optional tumor biopsy performed at end of treatment.

6: Includes recording of concurrent medications and focused physical exam. There is a +/- 4 day window allowable for each start of Cycle assessment.

7: Pill diary and remaining pills should be collected and new pill diary and 1 month supply of study drug should be given to patient.

8: One 10 cc tube of whole blood for gene expression analyses will be collected on Day 1 of Cycle 1 and Day 1 of Cycle 2

9: Blood for hormone levels (testosterone and estradiol) will be collected at start of treatment, Cycle 2, Day 1 and at end of treatment.

## **10.1 Research Tests**

### **10.1.a Research Bloods**

Serum testosterone level and estradiol level will be drawn on Cycle 1, Day 1 of treatment; Cycle 2, Day 1 of treatment, and at end of treatment. These will be collected as research non-billable blood draws. These tests will be performed and reported by the MSKCC central core laboratory. This testing is being performed to observe the effect of enzalutamide on testosterone and estradiol levels in women with ovarian, primary peritoneal, or fallopian tube cancer.

### **10.1.b Tumor Biopsy**

Tumor biopsies will be performed at two time points during this study; a biopsy will be performed at screening if no archival tissue is available and an optional biopsy will be performed at end of treatment.

If the patient has archival tissue available that is appropriate for AR IHC staining (block or unstained slides), then archival tissue may be used. In cases where multiple blocks are available staining will be performed on unstained slides from 3 separate blocks. If  $\geq 5\%$  AR tumor staining is seen on  $\geq 1$  slide the tumor will be considered to be AR+.

An optional tumor biopsy will be performed at end of treatment in those patients who have POD, consent to biopsy, and have accessible disease.

Biopsy samples should be fixed in 10% formalin and paraffin embedded. **In cases where a reasonable size biopsy is obtained (i.e., excisional biopsy, 18 gauge needle), such that the pathologist feels there is adequate sample for preparation of both a frozen and fixed specimen, a fresh frozen biopsy should also be collected.** At a minimum, enough tissue should be collected (by FNA or Core) for generation of a FFPE block for H&E and IHC analysis. At a maximum 2 cores should be collected.

Lesions with the greatest change in dimensional size based on interval evaluation are the recommended lesions to be excised. Whenever possible, biopsies at POD should be performed within 3 days of study drug discontinuation.

Biopsies obtained at the time of progressive disease will be used to investigate potential mechanisms of acquired resistance. Biopsy samples will be analyzed for level of AR positivity by IHC in order to determine if the androgen receptor is downregulated during treatment with enzalutamide.

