## 2.1 OBJECTIVES AND SCIENTIFIC AIM

Primary Objective:

- To estimate the proportion of women with AR(+) ovarian, primary peritoneal, or fallopian tube cancer who survive progression free for at least 6 months and the proportion of patients who have objective tumor response (complete or partial response) by RECIST 1.1 criteria when treated with enzalutamide 160 mg PO QD.

Secondary Objective:

- To determine the frequency and severity of adverse events as assessed by NCI CTCAE version 4.0 in women with AR (+) ovarian, primary peritoneal, or fallopian tube cancer treated with enzalutamide 160 mg PO daily.

Exploratory Objective:

- To perform optional tumor biopsies following treatment with enzalutamide, in order to determine the effect of treatment with enzalutamide on androgen receptor expression
- To observe the effect of enzalutamide on serum testosterone and estradiol levels in women with AR+ ovarian, primary peritoneal, or fallopian tube cancer.

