### **3.0 BACKGROUND AND RATIONALE**

#### **3.1 Androgen Receptor and Ovarian Cancer**

Ovarian cancer is the second most common gynecologic malignancy and the leading cause of death among women with gynecologic malignancies. There are an estimated 21,990 new cases and 15,460 cancer-related deaths from ovarian cancer in the United States annually [1]. Approximately 75% of women with epithelial ovarian cancer present with advanced (stage III or IV) disease. Standard treatment for women presenting with advanced ovarian cancer includes cytoreductive surgery followed by combination chemotherapy with platinum and taxane agents [2]. The majority of these women will recur and be treated with multiple lines of single-agent cytotoxic chemotherapy. Progression-free survival following first, second and third remission are 10.2, 6.4 and 5.6 months respectively[3]. Long-term survival among women diagnosed with advanced-stage ovarian cancer remains < 30%. Additional options for recurrent and persistent disease are clearly needed [4, 5].

Androgen receptors (ARs) are found in 67-90% of cases of epithelial ovarian cancer, and are more prevalent than estrogen (32-55% of cases) or progesterone receptors (46-52% of cases) in this disease [6-10]. Historically, studies targeting androgen inhibition in ovarian cancer using GnRH agonists or AR antagonists have shown a response rate of 0-22% and stable disease in 8-70% of women [11-20]. Our group at MSKCC published a negative phase II study of goserelin and bicalutamide consolidation therapy in patients with 2 or more prior therapies in 2007; androgen inhibition in ovarian cancer has largely been ignored since that time [21].

However, all clinical studies of androgen inhibition in ovarian cancer to date have been performed in an unselected population of patients with multiple lines of prior treatment. Recent preclinical data shows that primary cultures of AR+ ovarian cancer cells show an increase in cell division when exposed to androgen, and that this activity is reversed when androgen is inhibited[22]. In addition, androgen receptor positivity has been shown to decrease following chemotherapy, indicating that patients with multiple lines of prior treatment may be less likely to be AR+ and therefore less likely to respond to antiandrogen therapy.

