## **6.1 CRITERIA FOR SUBJECT ELIGIBILITY**

### **6.2 Subject Inclusion Criteria**

- Advanced or recurrent epithelial ovarian, fallopian tube or primary peritoneal carcinoma. Histologic documentation of the original primary tumor is required via the pathology report
- AR expression  $\geq 5\%$  by IHC. In cases where multiple blocks are available staining will be performed on unstained slides from 3 separate blocks. If  $\geq 5\%$  AR tumor staining is seen on  $\geq 1$  slide the tumor will be considered to be AR+.
- Patients with the following histologic cell types are eligible: serous adenocarcinoma, endometrioid adenocarcinoma, mucinous adenocarcinoma, undifferentiated carcinoma, clear cell adenocarcinoma, mixed epithelial adenocarcinoma, transitional cell carcinoma, malignant Brenner's tumor, or adenocarcinoma not otherwise specified
- Measurable disease as defined by RECIST 1.1. Measurable disease is defined as at least one lesion that can be accurately measured in at least one dimension. Each lesion must be  $\geq 10\text{mm}$  when measured by CT, MRI or caliper measurement by clinical exam; or  $\geq 20\text{mm}$  when measured by chest x-ray. Lymph nodes must be  $\geq 15\text{mm}$  in short axis when measured by CT or MRI
- Patients must have had one prior platinum-based chemotherapeutic regimen for management of primary disease
- Patients may have received, but are not required to have received, one or two additional cytotoxic regimens for management of recurrent or persistent disease
- Patients who have received only one prior cytotoxic regimen (platinum-based regimen for management of primary disease), must have a platinum-free interval of less than 12 months, or have progressed during platinum-based therapy, or have persistent disease after a platinum-based therapy
- Patients are allowed to receive, but are not required to receive, non-cytotoxic therapy (such as bevacizumab) as part of their primary treatment regimen. Patients are allowed to receive, but are not required to receive, non-cytotoxic therapy for management of recurrent or persistent disease

- Must be  $\geq 18$  years of age
- Karnofsky Performance Status (KPS) of  $\geq 70\%$
- Life expectancy of  $\geq 12$  weeks
- Women of child-bearing potential must have a negative pregnancy test within 14 days prior to commencement of study treatment

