### 14.3. Other objectives

Safety and tolerability will be summarized using descriptive statistics. Adverse events will be assessed by NCI CTCAE version 4.0 criteria. The serious adverse events will be described separately.

The PFS duration will be summarized using the Kaplan-Meier method and the median PFS time will be estimated.

The treatment outcomes such as response rate and PFS will be associated with the AR expression (actual expression level, on a scale from 0-100%) by using Wilcoxon two sample test for relating to response and Cox PH model for relating to PFS.

The effect of enzalutamide (continuous) on levels of serum estradiol and testosterone and the effect on tumor AR expression by IHC will be described in graphical form and with descriptive statistics.

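### A fall in AR expression from archival tissue to the end-of-treatment biopsy cannot be attributed to enzalutamide, because the archival tissue may predate chemotherapy and the baseline AR value is undefined

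*Combined protocol and SAP*

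**What the plan says.** Section 2.1 lists optional biopsies after treatment as an exploratory objective, "in order to determine the effect of treatment with enzalutamide on androgen receptor expression". Section 10.1.b puts the question more sharply: the samples are stained "in order to determine if the androgen receptor is downregulated during treatment with enzalutamide". Section 14.3 plans no test; "the effect on tumor AR expression by IHC will be described in graphical form and with descriptive statistics".

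The pre-treatment side of the comparison comes from screening. Section 10.1.b permits stored tissue, "If the patient has archival tissue available that is appropriate for AR IHC staining", and "a biopsy will be performed at screening if no archival tissue is available". Sections 4.2 and 4.3 agree. Where several blocks exist, slides from three are stained, and 5% staining on any one of them makes the patient eligible (Sections 4.3, 6.2 and 10.1.b).

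On prior treatment, Section 6.2 states: "Patients must have had one prior platinum-based chemotherapeutic regimen for management of primary disease". One or two further cytotoxic regimens are allowed. Section 3.1 states that "androgen receptor positivity has been shown to decrease following chemotherapy"; Section 3.5 says only that AR expression may be lower after several lines.

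**The concern.** To say that AR went down during treatment, one needs a value from just before treatment. Most patients may have only a stored specimen, possibly from the original surgery, with chemotherapy given between that specimen and day 1. By the protocol's own account such chemotherapy lowers AR positivity, so the plan cannot separate its effect from that of the study drug.

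A second problem is that the baseline number is not defined. Patients enter on any one positive slide out of up to three. If the highest slide were also taken as the patient's AR level, a later single reading would tend to be lower with no biological change. The same undefined value enters the Wilcoxon and Cox analyses of Section 14.3, which use the actual expression level from 0 to 100%.

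At stake is the answer to one exploratory objective. Neither primary endpoint nor any stopping rule depends on it.

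**Working it through.** The plan states no sample size, expected change or test for the AR comparison, so there is no figure to reproduce.

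**Step 1: which tissues are compared.** The only tissue time points are screening and end of treatment (Section 10.1.b and the Section 10.0 schedule). No section limits the age of archival tissue, requires it to follow the last chemotherapy, or asks for its date. Every patient has had 1 to 3 cytotoxic regimens, so 0 to 3 of them may lie between the baseline tissue and day 1.

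**Step 2: the chemotherapy part.** The observed change is the change due to intervening chemotherapy, plus the change on enzalutamide, plus sampling error. Section 3.1 gives the first term a downward direction but no size. It is zero for patients with a fresh screening biopsy and for those whose archival tissue follows their last regimen. The documents do not say how many these are.

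**Step 3: the slide-value part.** Suppose nothing changes over time. If three baseline readings and one later reading are exchangeable and untied, each is equally likely to be the highest, so P(later reading < highest of three) = 3/4.

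For the size, let logit(AR) = m + b + e, with b varying between patients and e between slides of one tumour. Patients enter if any baseline slide is at least 5%. All variability inputs are assumptions. With m = 0 and 1,000,000 simulated patients per setting:

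| SD between / within | Highest of 3 vs 1 later | Mean of 3 vs 1 later | 1 vs 1 | Highest of 3 vs highest of 3 |
|---|---|---|---|---|
| 1.2 / 0.5 | fall 8.0 points | 0.0 | fall 0.1 | 0.0 |
| 1.2 / 0.75 | fall 11.7 | 0.0 | fall 0.1 | 0.0 |
| 1.5 / 1.0 | fall 14.0 | 0.0 | fall 0.5 | fall 0.1 |

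Across m from -0.5 to 0.5 and all combinations of between-patient SD 1.2 or 1.5 with within-tumour SD 0.5, 0.75 or 1.0, the first column runs from 7.1 to 15.0 points and the one-slide column from 0.0 to 0.8.

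A wider set of assumptions uses total logit SD 2, slide correlation 0.5 to 0.9, and 67%, 80% or 90% of single slides at or above 5% (the outer values borrowed from the AR prevalence range in Section 3.1). It gives falls of 7.9 to 19.1 points for the highest of three, 0.0 to 0.5 for the mean of three, and 0.2 to 4.2 for one slide. The last range is regression to the mean from the 5% entry floor alone.

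**Step 4: who supplies the pairs.** Under Section 10.1.b the later biopsy comes only from consenting patients with progression and accessible disease, and the lesion with the greatest size change is preferred. Nothing matches it to the archival site. The direction of any bias from this is unknown.

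**The case against.** The strongest reply is that the slide artefact rests on a rule the plan does not contain. The any-slide rule only classifies a tumour as AR-positive. Section 10.2 reports percent of cells staining and Section 14.3 uses the actual level; neither says highest. Section 10.2 also speaks of one to three slides for all tissue, and up to two cores are allowed at follow-up, so three slides against one is itself an assumption. This stands: what is shown is an unspecified value, not a built-in fall.

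The 3/4 result also needs untied readings. In the three tabulated settings, rounding to 5-point steps lowers it to about 66 to 69%, and to 10-point steps about 58 to 64% (step sizes assumed).

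The statement on chemotherapy in Section 3.1 carries no citation and concerns positivity rather than a patient's percentage, and Section 3.5 is more cautious. With the unknown effect of taking only progressors and choosing lesions by size change, the net direction of bias is less certain than the chemotherapy argument alone suggests. This also stands.

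Finally, the aim is exploratory, the biopsy optional and the analysis descriptive. That limits the severity. It does not make the attribution to enzalutamide valid, since graphs of the raw difference would still show chemotherapy and drug effects together.

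A reader might also infer that AR status at entry is outdated and that the selected population, and so the primary analysis, is compromised. The documents give no figure for this, and screening on archival tissue is a feasibility choice.

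**Conclusion.** The point holds as a minor one. Under the plan as written, a fall from archival tissue to the biopsy at progression cannot be attributed to enzalutamide, because chemotherapy given in between is an alternative explanation that the protocol itself supplies. That rests on the text alone; the size of the effect cannot be derived from the documents.

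The added artefact depends on an unstated choice. With no true change it is about 8 to 14 points if the highest of three slides is set against one later slide. It is about 0 to 1 point with the mean of the slides or one slide at each time, and up to about 4 points for one slide under wider assumptions. These figures rest on assumed variability.

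It would go too far to conclude that the comparison must show a fall, that three quarters of patients will show one, or that the overall bias has a known direction.

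**What to change.** Amend Sections 10.1.b and 14.3 and leave the eligibility rule in Section 6.2 as it is. Changing which specimen decides entry could alter the enrolled population and the screen failures, and this point does not need it.

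1. Record the collection date of the baseline tissue and the cytotoxic regimens given between collection and day 1.
2. Define the AR value as the mean percent staining across slides, at both time points and in the Wilcoxon and Cox analyses.
3. Report pairs whose baseline tissue was taken after the last cytotoxic regimen (including fresh screening biopsies) separately from the others. Draw any downregulation statement only from the former, and describe the others as change since the archival sample.
4. State that pairs come only from consenting progressors with accessible disease, with the lesion chosen by size change, and that this may bias the comparison in an unknown direction.

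The cost is a few sentences and two data fields, with no new procedure. The downside is that few pairs may support a downregulation statement; the documents do not let one count them. Averaging does not help patients with a single baseline slide, for whom the small regression to the mean remains.
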